## 4.2 EVALUATION OF THE BEHAVIOUR AND EXPERIENCE OF THE MOBILIZING PROFESSIONALS

- How do professionals involved in early mobilization and positioning of ICU patients experience the use of a robotic system for early mobilization?
- How do the mobilizing specialists in nursing, physiotherapy and medicine rate the robotic system for early mobilization of patients in the intensive care unit regarding the burden and relief during the mobilization?
- What consequences does the implementation of a robotic system for the early mobilization of patients in intensive care units have on the mobilization and positioning behavior of the nursing, physiotherapy and medical staff involved?

Episodic interviews	Subjectively perceived emotions (such as stress) of the mobilizing professionals during positioning and mobilization without (T1) and with (T2 and T3) the robotic system.
	Recording of the motivating and challenging factors of the mobilizing professionals during positioning and mobilization without (T1) and with (T2 and T3) the robotic system.
	Subjectively perceived physical strain of the mobilizing professionals during positioning and mobilization without (T1) and with (T2 and T3) the robotic system.
Standardized observation	Behavior of the mobilizing professionals during positioning and mobilization without (T1) and with (T2 and T3) the robotic system
	Body posture of the mobilizing professionals during positioning and mobilization without (T1) and with (T2 and T3) the robotic system
	Personnel effort during positioning and mobilization without (T1) and with (T2 and T3) the robotic system
	Secondary data of patients (T2 and T3) who are mobilized (from the study arm effects on patient outcomes).

## 4.3 EVALUATION OF THE EFFECTS ON PATIENT OUTCOMES

- Can robot-assisted early mobilization improve muscle strength and reduce muscle loss compared with the historical collective?
- Can robot-assisted early mobilization reduce the duration of ventilation?  
In addition, further questions will be addressed:
- Does robotic-assisted early mobilization result in changes in consciousness, pain, cognition, health perception, cardiocirculatory and respiratory function, other factors such as pressure ulcers, bowel emptying, insulin requirements, and duration of treatment?

For this purpose, the following outcome criteria of the patients are examined.

Primary outcome criteria	Physical function/muscle strength	Surveyed according to the MRC (Medical Research Council) classification on upper and lower extremity and using the FSS-ICU (32, 33) at discharge ICU.
	Parameters for the assessment of muscle deterioration	Muscle thickness of quadriceps femoris muscle (thickness quadriceps femoris muscle and cross sectional area rectus femoris muscle)  Muscle thickness of the diaphragm / Thickening fraction diaphragm  Diaphragm mobility at discharge ICU
	Ventilation time	Duration (d) of invasive ventilation

Secondary outcome criteria	Consciousness/ cognition/ pain/ health perception	Pain using the Visual Analog Scale (VAS) (before and after mobilization).  Delirium incidence using the CAM ICU (34): number of days without delirium.  Sedation level using the Richmond Agitation Sedation Scale (RASS)(35)  level of consciousness using the Glasgow Coma Scale (GCS) (36)  Health-related quality of life after 3 months using the SF-36 questionnaire (37)
	Hemodynamics	Blood pressure / catecholamine demand / heart rate / cardiac output / oxygen consumption
	Respiration	CPAx-respiratory function(38) / oxygenation index / lung ultrasound parameter
	Others	Intestinal evacuation (yes/no)  Decubitus (grade classification 1-4 according to Shea (39))  Lactate level before and after mobilization (if laboratory value available)  Insulin requirement
	ICU Scores	SOFA [39] / Apache II (40) / SAPS II (41)  Intensive care unit treatment duration / inpatient treatment duration

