- (2) The behavior and experience of the mobilizing professionals will be evaluated using episodic interviews as well as standardized observations. Nurses with specialized training in anesthesia and intensive care, nurses and physiotherapists who have at least three years of professional experience in an intensive care unit as well as medical specialists who have completed their training as medical specialists or who have a leading position in an intensive care unit are included. In addition, the individuals have an employment contract at LMU Klinikum. Furthermore, the secondment to the anesthesiological intensive care units is an inclusion criterion.
- (3) The effects on patient outcomes, primarily duration of ventilation, muscle mass (sonographic examination) and physical activity (measured by established scores such as FSS-ICU and MRC classification), will be measured at different points in time and compared with a historical patient population. Secondary outcomes such as delirium incidence, hemodynamic parameters, respiratory parameters but also longitudinal parameters such as intensive care and hospital length of stay will be analyzed from routine data/patient records. Included are informed consenting patients who will undergo a planned surgical procedure that involves postoperative intensive treatment and an anticipated duration of ventilation of more than 48 hours. These patients will receive standardized early mobilization using the robotic system at either ten frequencies or for seven days. No invasive procedures such as blood sampling will be performed as part of the study. To evaluate the effect of robot-assisted VEM, the outcomes

will be compared with a historical comparison group. Approximately 30 patients shall be included. The results will be compared to a historical group (n=30) with conventional early mobilization.

The intervention is planned for a duration of five to six months starting in August 2021.

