#### *Exclusion criteria*

- Patients refusal to participate in the study
- unable to give informed consent
- chronically bedridden before inclusion
- clinical frailty scale  $\geq 7$  (42)
- chronic ventilation (more than 24 hours) before admission to the intensive care unit
- Elevated intracranial pressure / risk for elevated intracranial pressure / recent cerebral hemorrhage
- Pregnancy
- Pre-existing neuromuscular disease resulting in chronic limitation of strength and performance
- Sternotomy / Sternectomy during a surgical procedure

Patients meeting the following criteria will be retrospectively selected for the historical comparison group:

- planned surgical procedure
- Postoperative intensive care and therapeutic treatment
- Duration of ventilation > 48 hours
- age  $\geq 18$  years
- Weight >45 kg and <135 kg
- Body height >1.50 m and <1.95 m
- Patients who met any of the exclusion criteria during their intensive care unit stay will not be included in the historical group.

No matching is planned.

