## 10. ETHICAL CONSIDERATION FROM THE PERSPECTIVE OF THE STUDY TEAM

The study itself is designed as a clinical intervention study with comparison to a historical patient population. Patient participation is voluntary. The value of early mobilization in critically ill patients has been proven, as has the safety of early mobilization. Harmful events occurred very rarely in comparable studies, and serious adverse events seen in association with the study did not occur (5, 16). The use of the VEMO© system has also been studied and found to be safe. Thus, participating patients have no a priori disadvantage. The VEMO© system has a CE certificate and is approved for the early mobilization of critically ill patients. It is categorized as a class 2a medical device and is in regular use in several German and international hospitals, such as the Berufsgenossenschaftliche Unfallklinik Murnau, the Schön Klinik Bad Aibling or the Universitätsmedizin Charité Berlin. The system is only used for the approved indication (early mobilization of critically ill patients). A hygiene concept for the application of the system was developed in cooperation with the hospital hygiene department. The surveys within the scope of organizational feasibility accompany the interventions and pose no risk to patients through the observational function.

Otherwise, the study team has no influence on the treatment of the patients.

The primary benefit in terms of effects on patient outcomes is to determine whether robot-assisted mobilization differs from conventional early mobilization in its ability to reduce ventilation time, muscle atrophy, and intensive care unit (ICU)-acquired weakness.

Individual patients could benefit from intensive robot-assisted early mobilization in terms of shorter ventilation, less muscle atrophy, and better physical functionality. A lasting negative impact in the patient group is not expected if treatment with a safe, non-invasive medical device and intensive physiotherapeutic exercise is performed. Serious adverse events associated with the medical device are not known. Possible adverse events such as short-lasting changes in blood pressure and heart rate, the accidental removal of drains or the development of skin lesions due to the mobilization cuffs could occur.

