From the data obtained, improved therapy concepts can be developed and the use of robot-assisted mobilization can be established as part of a new standard of care. This study makes a significant contribution to a future improvement of therapy for critically ill patients. If the measures of robot-assisted VEM prove to be superior to the measures of historical, conventional VEM, the new treatment technique could be quickly implemented in the clinical routine of intensive care units on the basis of the project presented here.

The data collected during the study are not available to the treating physicians during the patient recruitment phase. This way, in particular, no negative influence on the therapy of the individual patient can arise. Even if conclusions regarding the treatment of future patients or patients from other intensive care units cannot be drawn from the data obtained in an unlimited and uncritical manner, the study presented here provides a valuable gain in knowledge with the aim of comparatively examining different forms of early mobilization of the effect on a specific patients population. By simultaneously surveying the experience and behavior of the mobilizing professionals, it is also possible to record their workload when using the new therapy. Given the high workload in intensive care units, a feasibility study is essential, so the focus of this study is on users, patients, and structures.

In summary, this study makes an important and necessary contribution to improving the therapy of critically ill patients. There are no study-related burdens for the individual patients and participation in the study is without risks for the patients.

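### Two of the three primary patient-outcome domains may have no comparable values in the historical group, and the third, ventilation time, is compared under different entry rules

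*Protocol*

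**What the plan says.** **Promised comparison.** Section 4.3 asks "Can robot-assisted early mobilization improve muscle strength and reduce muscle loss compared with the historical collective". The executive summary says that ventilation time, muscle mass and physical activity "will be measured at different points in time and compared with a historical patient population", and adds: "The results will be compared to a historical group (n=30) with conventional early mobilization". Section 10 gives the main purpose of this arm as finding out whether robot-assisted mobilization "differs from conventional early mobilization in its ability to reduce ventilation time, muscle atrophy, and intensive care unit (ICU)-acquired weakness".

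**Primary outcomes (section 4.3).** There are three domains:
- strength/function: the MRC "classification on upper and lower extremity and using the FSS-ICU (32, 33) at discharge ICU";
- muscle deterioration: ultrasound of quadriceps and diaphragm, at ICU discharge;
- days of invasive ventilation.

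**Source for the controls.** Section 7.2 states: "Patients meeting the following criteria will be retrospectively selected for the historical comparison group". Section 8 (Conventional early mobilization) takes their outcome criteria from routinely collected data. The list of data that follows identifies the electronic patient record as the place where routine information is held. No other control source is named.

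**Status of the examinations.** The table in section 8.3 marks the physical-function examination and the sonography of lungs, diaphragm and quadriceps as study-related. The text on FSS-ICU and MRC says that the study requires these scores. The schedule in section 8, including day -1, belongs to the study.

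**Entry.** For robot patients, section 7.2 asks for an expected ventilation time above 48 hours. For controls it lists an actual ventilation time above 48 hours, and plans no matching. Section 8 nevertheless says that the historical group also meets the study's inclusion and exclusion criteria.

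**The concern.** The data source named for the controls does not fit the examinations to be compared. If the protocol is followed as written, the strength and muscle comparisons may have no control values. Or they may have values only from controls whom somebody chose to examine, at times nobody fixed. The difference would then mix the effect of the robot with who was measured and when. Muscle loss also needs a starting value, and the day -1 examination is part of the study schedule. An analysis plan can handle partly missing data, but it cannot supply examinations that were never done.

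Ventilation time should be in the record, because controls are selected on it. That selection creates its own problem: every control exceeds 48 hours by construction, while a robot patient extubated earlier than expected stays in with a shorter time.

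The comparison carries weight. Section 10 says that if the robot-assisted measures "prove to be superior to the measures of historical, conventional VEM, the new treatment technique could be quickly implemented" in routine care. The feasibility and staff-experience arms are not affected.

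**Working it through.** **1. Outcomes resting on study-related examinations.** Section 4.3 lists MRC, FSS-ICU, quadriceps thickness, rectus femoris area, diaphragm thickness, thickening fraction, diaphragm mobility and ventilation duration: 8 measures in 3 domains. Section 8.3 places the first 7 under study-related examinations. That is 7 of 8 measures (8 of 9 if upper and lower extremity MRC count separately) and 2 of 3 domains.

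**2. The plan's own sample size.** Section 7.3 needs 50 subjects and adds 10% for drop-out: 50 × 1.10 = 55, as stated (50/0.90 = 55.6, rounded up to 56). With 30–35 robot patients, 55 − 30 = 25 and 55 − 35 = 20, so 20–25 controls remain. The executive summary gives 30.

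**3. Detectable difference by number of controls with a value.** Inputs: 30 robot patients, m controls with a value, two-sided 5% t-test (sidedness and test assumed), 80% power. The normal approximation is d = (1.96 + 0.84) × √(1/30 + 1/m). The noncentral t-distribution gives slightly larger values, which are used below.

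| m | approximation (SD) | t-test (SD) |
|---|---|---|
| 30 | 0.72 | 0.74 |
| 25 | 0.76 | 0.77 |
| 20 | 0.81 | 0.83 |
| 15 | 0.89 | 0.91 |
| 10 | 1.02 | 1.05 |
| 5 | 1.35 | 1.39 |
| 0 | no comparison | no comparison |

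The rows for 20–25 are the case of complete control data under section 7.3, and the row for 30 is the same case under the executive summary. The rows for 15, 10 and 5 are assumptions, because the protocol does not say how many controls have a value. The table shows lost precision only, not the bias from selective measurement.

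**4. Ventilation time with no true effect.** Let p be the share of robot patients ventilated for 48 hours or less. Assume that the other robot patients have the same distribution as the controls. A robot patient at or below 48 hours is shorter than every control (probability 1); any other is shorter with probability 1/2. Hence

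P(robot shorter) = p × 1 + (1 − p) × 1/2 = (1 + p)/2.

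The protocol does not give p. For an assumed 10%, 20% and 40% (3, 6 and 12 of 30) the result is 0.55, 0.60 and 0.70, against 0.50 without the mismatch.

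**5. What that does to a test.** Section 9 names only robust methods in general, so a two-sided 5% rank-sum test is assumed. In 20,000 simulated comparisons of 30 against 30, with no true effect, the result was significant in favour of the robot in about 9–10% (p = 10%), 25–27% (p = 20%) and 78% (p = 40%) of runs. The nominal figure is 2.5%.

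**The case against.** The strongest reply is that the gap is inferred. Section 8 says that the controls' outcome criteria come from routine data, which presupposes that they are there. Section 8.3 describes what is done to enrolled patients and classes it by study burden; it does not describe old records. This stands in part. A reader might infer that the records hold no MRC, FSS-ICU or ultrasound values. The documents do not say so, and some values may exist. But they also give no basis for assuming values at ICU discharge, a preoperative baseline, or values in all controls.

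A reader might also take the condition on lactate, "Lactate level before and after mobilization (if laboratory value available", as a sign that the authors considered availability there and overlooked it for the muscle outcomes. That does not follow. The study rules out its own blood sampling, which explains the condition.

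On ventilation time, section 8's general statement that controls meet the study criteria could be read as removing the mismatch. It does not: the explicit list in section 7.2 uses actual duration, so the two passages conflict. It is fair that p is unknown, and that the formula needs groups that are otherwise alike, which is not assured without matching. A reader might infer that any ventilation advantage must be an artefact; the documents do not support that either.

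Finally, feasibility is the leading aim, and section 10 itself cautions against uncritical generalization. That limits the scope of the point, but these outcomes are still labelled primary in their arm.

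**Conclusion.** The point holds as a conflict between the promised comparison and the named data source. Two of the three primary domains may lack comparable control values or rest on selectively measured controls; actual availability is unknown. The third domain has an entry mismatch. With otherwise alike groups and no true effect, it lifts the probability of a shorter time under the robot from 0.50 to 0.55–0.70, if 10–40% of robot patients are ventilated for 48 hours or less. The test error rates also depend on that assumed share and on the assumed test. Even with complete control data, the 20–25 controls implied by section 7.3 allow detection of only about 0.77–0.83 SD with 30 robot patients. As written, none of the three primary comparisons with the historical group is secure.

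**What to change.** 1. **Check the records before any outcome comparison.** Name in section 8 (Conventional early mobilization) the primary outcomes that were routinely recorded at ICU discharge in the historical group. Compare between groups only outcomes measured as routine in essentially all eligible controls, by a threshold fixed before outcomes are seen. Treat outcomes measured in only some controls as descriptive.

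2. **Outcomes that fail the check.** Report strength/function or ultrasound for the robot group only, with the discharge value and the change from day -1, which the section 8 schedule already collects. Remove the between-group wording for these outcomes from the executive summary, section 4.3 and section 10. Outcomes that pass keep their present wording.

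3. **Reconcile the entry rules in sections 7.2 and 8.** Select controls by the preoperative expectation of more than 48 hours of ventilation where the record allows it. Otherwise, report the share of robot patients ventilated for 48 hours or less and add a sensitivity analysis limited to patients above 48 hours in both groups. State that this analysis conditions on an outcome that treatment may already have affected, since robot sessions can start before 48 hours. The ventilation comparison is then not evidence of superiority by itself.

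**Cost.** One record check, a few changes of wording and one aligned entry rule; no new patient examinations. The ethics committee must be consulted (Obligation of the study management). The between-group muscle claim may have to be given up, and within-group changes cannot be attributed to the robot.

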### 7.3. NUMBER OF PATIENTS

In order to test correlations using multiple-variate models (multiple linear regressions) with a statistical power of 80% on approximately 8 independent variables (UV) compared to the dependent variable (AV), an approximate total sample size of 50 subjects is required.

Thus, with an expected drop-out of 10%, 55 patients (robotic intervention and historical comparison group) should be included in the study. A sample size of 20 subjects is considered a lower limit with moderately strong associations between UVs and AV and inclusion of a maximum of 5 UVs, with  $\alpha=5\%$  and  $\text{power}=80\%$  (43, 44). In this regard, if 30-35 patients are included in the robot-assisted intervention and a maximum of 6 UVs, meaningful results can be expected to be obtained in a manageable period of time.

All patients will be included in the intervention only if written informed consent is obtained. Due to the expected patients' recruitment (6-8 patients/month) with a given number of cases (30-35 patients in the intervention), the study is expected to last five to six months from the start. The recruitment rate depends on the number of patients.

In general, all patients meeting the above-mentioned criteria will be included in the study. The study is completed as soon as the required number of patients has been recruited for the intervention. The corresponding number of cases for the historical group will be taken from the routine data.

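### Section 4.3 labels eight or nine patient measures as primary without ranking them, while section 7.3 sizes the study for one unnamed dependent variable

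*Protocol*

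**What the plan says.** Protocol section 4.3 has one block labelled "Primary outcome criteria" with three domains:

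- Physical function and strength: "Surveyed according to the MRC (Medical Research Council) classification on upper and lower extremity and using the FSS-ICU (32, 33) at discharge ICU".
- Muscle deterioration: for the thigh, "thickness quadriceps femoris muscle and cross sectional area rectus femoris muscle"; for the diaphragm, "Muscle thickness of the diaphragm / Thickening fraction diaphragm" and "Diaphragm mobility at discharge ICU".
- Ventilation time: "Duration (d) of invasive ventilation".

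The executive summary (section 1) repeats three domains as primary, again in no order of importance.

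Section 7.3 gives 80% power for multiple linear regression "on approximately 8 independent variables (UV) compared to the dependent variable (AV"), which leads to 50 subjects, raised to 55 for 10% drop-out. It does not say which outcome that variable is. A significance level of 5% is written only in the later sentence on a lower limit of 20 subjects and at most five predictors.

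Section 9 says that the two forms of mobilization will be compared with robust methods in common use. It does not single out an outcome. Section 10 looks ahead to possible adoption in routine care: "If the measures of robot-assisted VEM prove to be superior to the measures of historical, conventional VEM".

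**The concern.** The primary outcome is the measure on which a claim of benefit rests and for which the study is sized. Here the two sections do not meet: one lists eight or nine co-equal measures, and the other uses a single unnamed one. A reader cannot tell which measure the 50 subjects serve, or which result, or how many results, would answer the question put in section 4.3.

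The practical risk is selection after the fact. With no ranking, a favourable result on any one measure could be reported as a benefit on a primary outcome. A 5% level for a single test does not describe the error rate of that claim. The choice of primary outcome belongs in the protocol, because the sample size depends on it, so a separate SAP would not remove the mismatch.

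**Working it through.** **1. Count of primary measures (section 4.3)**

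| Domain | Measures | Count |
|---|---|---|
| Function/strength | MRC (one score, or two if split by extremity), FSS-ICU | 2 or 3 |
| Thigh muscle | quadriceps thickness, rectus femoris area | 2 |
| Diaphragm | thickness, thickening fraction, mobility | 3 |
| Ventilation | days of invasive ventilation | 1 |
| Total | | 8 or 9 |

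Section 3.1 also calls feasibility measures and adverse events primary. They are mainly descriptive and are not counted here.

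**2. The plan's own figure (section 7.3)**

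The drop-out step reproduces: 50 × 1.1 = 55. Dividing instead gives 50 / 0.9 = 55.6, or 56, a difference of one patient.

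The 50 cannot be reproduced uniquely, because no effect size is given and its sentence states no alpha. Assuming alpha 5%, 80% power and 8 predictors, the noncentral F distribution (noncentrality f² × N) gives for N = 50:

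- overall test of all predictors: f² = 0.36, that is R² = 0.36 / 1.36 = 0.265;
- test of one coefficient, such as treatment group: f² = 0.165.

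Neither can be tied to a listed measure, so the calculation does not show which outcome was meant.

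**3. Family-wise error if the list is used as it stands**

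Assumptions, none of them stated in the protocol: each measure is tested two-sided at 5%, there is no true effect, and any one positive result is claimed.

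For k independent tests, the error is 1 − 0.95^k:

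- k = 3 (one test per domain): 1 − 0.857 = 14.3%
- k = 8: 1 − 0.663 = 33.7%
- k = 9: 1 − 0.630 = 37.0%

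The measures come from the same patients and several from the same muscle, so positive correlation is likely. The protocol gives no correlations. Simulation of normal test statistics with a common correlation (400,000 draws) gives:

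| Common correlation | 8 measures | 9 measures |
|---|---|---|
| 0 | 33.7% | 37.0% |
| 0.3 | 30.0% | 32.7% |
| 0.5 | 24.9% | 26.8% |
| 0.7 | 19.1% | 20.3% |
| 0.9 | 12.0% | 12.4% |

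One named primary measure gives 5%.

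**4. How many comparisons are possible**

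Section 8 (conventional early mobilization) takes the historical group's outcomes from routine records. Section 8.3 lists the physical-function and ultrasound examinations as study-related. Some of the eight or nine measures may therefore not exist for the historical group. The protocol does not settle how many do. If only ventilation time could be compared, there would be one test and no inflation, but most of the listed primary measures could then not answer the comparative question.

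**5. Ventilation duration as the candidate**

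Section 7.2 enrols the robot group on an expected ventilation time above 48 hours and selects the historical group on an actual time above 48 hours. Historical patients ventilated for 48 hours or less are removed by selection. Robot-group patients who come off the ventilator that early can stay. The mismatch therefore shortens ventilation in the robot group relative to the historical group, even with no treatment effect.

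**The case against.** The strongest case on the other side has four parts.

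- **The study is largely exploratory.** Section 3 puts feasibility first, and section 9 plans plots, correlations and general comparisons. Family-wise error is a criterion for confirmatory claims, and a multiplicity method is commonly left to the SAP. The absence of such a method is accordingly not the point made here. Section 6, however, makes the comparison with historical patients a design aim, and section 4.3 did choose primary outcomes without reducing them to what section 7.3 sizes.
- **The singular dependent variable is ordinary regression wording.** Each model has one. This is fair: it does not prove that the authors had a single endpoint in mind. It still leaves the sample size tied to no listed outcome.
- **Section 10 is conditional.** A reader might infer that it commits the team to a superiority claim on any outcome followed by quick adoption. It does not. The sentence begins with a condition, its word for measures most naturally means the treatments, and the same section warns against uncritical conclusions.
- **Fewer tests may be possible.** The high figures need eight or nine between-group comparisons, and the historical records may not support that many. This stands and limits the size of the problem.

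**Conclusion.** The point holds as a mismatch between sections 4.3 and 7.3: eight or nine unranked primary measures against one unnamed dependent variable, so no stated error rate covers a claim of benefit on a primary outcome.

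A reader might infer that the false-positive risk is simply one in three. The documents do not support that as a flat statement. It is the upper end, and it needs independent tests, an unadjusted 5% on every measure and an any-one-counts rule that the protocol nowhere states. Under the same rule, eight or nine measures give about 12% at a common correlation of 0.9, rising to 37% with independence; three independent domains give about 14%. Fewer available comparisons would lower these figures.

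Nor does section 7.3 fix 5% for the main calculation, since that level is attached only to the 20-subject lower limit. The point should be corrected, but it does not by itself invalidate the study.

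**What to change.** Either of two changes would do.

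1. Name one primary patient outcome, with its time point, that is available in both groups. State in section 7.3 that the sample size refers to it, with its alpha and assumed effect. List the other measures as secondary.
2. Keep several primary measures, limited to those available in both groups, and state that they are tested in a fixed order or with Holm's method.

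If ventilation duration is chosen, first reconcile the expected and actual 48-hour criteria in section 7.2. That goes beyond wording, because it may change who enters the comparison.

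Otherwise the cost is protocol text and a loss for the remaining measures. Under option 1 they lose primary status. Under option 2 they face a stricter level. Holm's first step uses 0.05 / 8 = 0.00625 or 0.05 / 9 = 0.00556. Guaranteeing the same power at that level, for the same effect, would multiply the sample size by about 1.63 or 1.66, from the squared ratio of (z for 1 − alpha/2 plus z for 80% power). A fixed order avoids the stricter level, but testing stops at the first non-significant measure.
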